8.5. Hypersensitivity/Anaphylaxis

Patients will be assessed for suspected anaphylaxis reaction during and after administration of the IMP (through 1 hour postdose) at visits 2, 3, and 4. Data will be summarized using descriptive statistics.

The number of patients with suspected anaphylaxis reactions and number of suspected anaphylaxis reactions per patient will be summarized using descriptive statistics.

The relative time of suspected event will be calculated as date/time of suspected event - date/time of most current IMP administration and summarized using descriptive statistics. If a patient has more than one suspected anaphylaxis reactions, the earliest time will be used for the calculation.

Data will be listed.

8.6. Electronic Columbia Suicide Severity Rating Scale

The eC-SSRS Baseline/Screening version will be completed at visit 1, and the eC-SSRS Since Last Visit version will be completed at all other visits (visits 2, 3, 4, and 5), including unscheduled visits. Any positive findings on the eC-SSRS Since Last Visit version require evaluation by a physician or doctoral-level psychologist.

Data for patients with positive findings (having suicidal ideation or suicidal behavior) will be listed.

8.7. Deaths

If any patient dies during the study, all relevant information will be discussed in the patient narrative included in the clinical study report.

8.8. Clinical Laboratory Tests

Clinical laboratory tests (serum chemistry, hematology, coagulation, and urinalysis; see protocol Appendix M) will be performed at all visits (visit 1 [screening] through visit 5 [EOT]) using the central laboratory. All clinical laboratory test results outside of the reference range will be judged by the investigator as belonging to one of the following categories:

- abnormal and not clinically significant
- abnormal and clinically significant

A laboratory test result that is judged by the investigator as clinically significant will be recorded on the source documentation and the CRF as an adverse event, and monitored as described in Section 7.1.2 of the protocol.

Laboratory test results will be presented in standard international (SI) units in summaries. Laboratory values and changes from baseline to each visit and Last Assessment will be summarized using descriptive statistics. Shifts (below [low], within [normal], and above [high] the normal range) from baseline to each postbaseline visit and the Last Assessment will be summarized using patient counts. Baseline is defined as the last observed data before the administration of the first dose of the IMP (also see Section 4.2).

The potentially clinically significant abnormal values will be derived using criteria specified in [Table 2](#) based on all postbaseline values (including scheduled, unscheduled, and withdrawal visits). The overall incidence of potentially clinically significant abnormal values will be summarized for laboratory variables using descriptive statistics by treatment group. Listings for patients who have potentially clinically significant abnormal laboratory data will be presented.

Table 2: Criteria for Potentially Clinically Significant Laboratory Values

Test	Criterion value
Serum chemistry	
ALT	≥3x ULN
AST	≥3x ULN
ALP	≥3x ULN
GGT	≥3x ULN
LDH	≥3x ULN
BUN	≥10.71 mmol/L
Creatinine	≥177 μmol/L
Bilirubin (total)	≥34.2 μmol/L
Hematology	
Hematocrit	Men <0.37 L/L
	Women <0.32 L/L
Hemoglobin	Men ≤115 g/L
	Women ≤95 g/L
WBC counts	≤3 x 10 ⁹ /L ≥20 x 10 ⁹ /L
Eosinophils	≥10%
ANC	≤1 x 10 ⁹ /L
Platelet counts	≤75 x 10 ⁹ /L ≥700 x 10 ⁹ /L
Urinalysis	
HGB	≥2 unit increase from baseline
Glucose	≥2 unit increase from baseline
Ketones	≥2 unit increase from baseline
Total protein	≥2 unit increase from baseline

ALP=alkaline phosphatase; ALT=alanine aminotransferase; ANC=absolute neutrophil count AST=aspartate aminotransferase; BUN=blood urea nitrogen; GGT=gamma- glutamyl transpeptidase; HGB=hemoglobin; LDH=lactate dehydrogenase; RBC=red blood cell; ULN=upper limit of normal range; WBC=white blood cell

Serum beta-human chorionic gonadotropin (β-HCG) tests will be performed for all women of childbearing potential at visits 1 and 5. Urine β-HCG tests will be performed for women of childbearing potential at visits 2 through 4. Pregnancy test results will be listed.

Current menstruating status (yes or no) will be collected at all visits and listed.

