- n. The patient has a history of prior exposure to a monoclonal antibody targeting the CGRP pathway (AMG 334, ALD304, LY2951742, or fremanezumab). If patient has participated in a clinical study with any of these monoclonal antibodies, it has to be confirmed that the patient received placebo in order to be eligible for this study.
- o. The patient has any finding in the baseline 12-lead ECG considered clinically significant in the judgment of the investigator.
- p. The patient has any finding that, in the judgment of the investigator, is a clinically significant abnormality, including serum chemistry, hematology, coagulation, and urinalysis test values (abnormal tests may be repeated for confirmation).
- q. The patient has hepatic enzymes (ALT and AST) $>1.5 \times$ the upper limit of normal (ULN) range after confirmation in a repeat test, or the patient has suspected hepatocellular damage that fulfills criteria for Hy's law at screening.
- r. The patient has serum creatinine $>1.5 \times$ the ULN or evidence of clinically significant renal disease in the judgement of the investigator.
- s. The patient cannot participate or successfully complete the study, in the opinion of their healthcare provider or the investigator, for any of the following reasons:
 - mentally or legally incapacitated or unable to give consent for any reason
 - in custody due to an administrative or a legal decision, under tutelage, or being admitted to a sanitarium or social institution
 - unable to be contacted in case of emergency
 - has any other condition, which, in the opinion of the investigator, makes the patient inappropriate for inclusion in the study
- t. The patient is an employee of the sponsor/participating study center who is directly involved in the study or is the relative of such an employee.

- u. The patient has an active implant for neurostimulation used in the treatment of CH.
- v. The patient is a member of a vulnerable population (eg, people kept in detention).
- w. The patient has a history of alcohol and/or drug abuse that in the investigator’s opinion could interfere with the study evaluations or the patient’s safety.

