4. GENERAL ISSUES FOR DATA ANALYSIS

4.1. General

Descriptive statistics for continuous variables include count (n), mean, SD, standard error (SE), median, minimum, and maximum. In addition, for fremanezumab concentration percentage coefficient of variation (%CV) and geometric mean will also be calculated. Descriptive statistics for categorical variables include patient counts and percentages, and a missing category will be displayed as appropriate.

Summaries of potentially clinically significant abnormal values for clinical laboratory tests and vital signs values will include all postbaseline values (including scheduled, unscheduled, and early withdrawal visits).

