8.10. Vital Signs

Vital signs (pulse, systolic and diastolic blood pressure, and body temperature) will be measured at each (visit 1 through 5). Weight will be measured at visits 1, 2, and 5. Any vital sign value that is judged by the investigator as a clinically significant change (worsening) from a baseline value will be considered an adverse event, recorded on the source documentation and transcribed onto the CRF, and monitored as described in Section 7.1.2 of the protocol.

Vital signs (including weight) values and changes from baseline to each visit and the Last Assessment will be summarized using descriptive statistics. The incidence of potentially clinically significant abnormal values will be summarized for selected vital signs using descriptive statistics. Baseline is defined as the last observed data before the administration of the first dose of the IMP (also see Section 4.2).

Table 3 specifies the criteria for identifying vital signs as potentially clinically significant abnormal values. Note that in order to qualify as potentially clinically significant abnormal, a value needs to meet both criteria below: ie, have a value beyond the criterion value and a change of at least the magnitude specified in the change relative to baseline column. The potentially clinically significant abnormal vital signs values will include all postbaseline values (including scheduled, unscheduled, and early withdrawal visits) for the summaries.

Table 3: Criteria for Potentially Clinically Significant Vital Signs

Vital Sign	Criterion value	Change relative to baseline
Pulse	≥120 bpm	Increase of ≥15 bpm
	≤50 bpm	Decrease of ≥15 bpm
Systolic blood pressure	≥180 mm Hg	Increase of ≥20 mm Hg
	≤90 mm Hg	Decrease of ≥20 mm Hg
Diastolic blood pressure	≥105 mm Hg	Increase of ≥15 mm Hg
	≤50 mm Hg	Decrease of ≥15 mm Hg
Temperature	≥38.3°C	Change of ≥1.1°C

bpm=beats per minute

Height will be measured at screening visit, and data will be listed in the vital sign listing.

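### The laboratory incidence table in SAP 8.8 does not separate chemistry and haematology abnormalities present before dosing from those that first appear on treatment; a new-onset count should be added beside it

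*SAP*

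**What the plan says.** SAP 4.1 sets the general rule: "Summaries of potentially clinically significant abnormal values for clinical laboratory tests and vital signs values will include all postbaseline values", with scheduled, unscheduled and early withdrawal visits all included. SAP 8.8 repeats it for laboratory data and applies the limits in SAP Table 2. The output is then: "The overall incidence of potentially clinically significant abnormal values will be summarized for laboratory variables using descriptive statistics by treatment group." A listing of the patients concerned is also planned.

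Every chemistry and haematology row of Table 2 is an absolute limit or a multiple of the upper limit of normal (ULN), for example 3 times ULN for GGT and 10% for eosinophils. No row refers to the baseline value. Other safety summaries in the SAP do look back to baseline:

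- The four urinalysis rows of the same table require a "≥2 unit increase from baseline".
- For vital signs (SAP 8.10, Table 3), "a value needs to meet both criteria below: ie, have a value beyond the criterion value and a change of at least the magnitude specified".
- Adverse event summaries (SAP 8.3) are limited to events starting at or after the first dose.

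The laboratory shift tables in SAP 8.8 do use baseline, but on a different scale: "Shifts (below [low], within [normal], and above [high] the normal range) from baseline to each postbaseline visit and the Last Assessment".

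**The concern.** A table of incidence by treatment group is naturally read as the rate of abnormalities arising on treatment. Here it mixes two groups: patients who crossed a limit after dosing, and patients who were beyond it before dosing and stayed there. The second group says nothing about the drug.

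Randomisation spreads these patients evenly across arms in expectation, so they form a common background in every column. That background makes a real increase look proportionally smaller. With about 100 patients per arm (protocol 3.2), chance imbalance in the background can also blur a small excess or imitate one. Evaluating safety is a stated secondary objective (protocol 2.1), and the data needed to separate the two groups are collected at every visit.

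**Working it through.** The plan states no figure for this point, so there is none to reproduce. The check has three parts.

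**1. Does any planned output give the new-onset rate?**

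- Incidence table: no baseline condition, so no.
- Shift tables: they use low, normal and high against the reference range. A GGT rising from 1.2 to 4 times ULN and one staying at 4 times ULN both appear as high to high.
- Change-from-baseline statistics: these describe group averages, not patients crossing a limit.
- Listing: it shows individual patients but gives no rate by arm.

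**2. Which tests can be beyond a limit at baseline?**

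- ALT and AST: protocol 4.2 excludes confirmed values above 1.5 times ULN, and Table 2 starts at 3 times ULN. Protocol Appendix J, however, describes patients with baseline values from 2 up to 3 times ULN as enrollable. The two passages conflict and must be reconciled. Even on the Appendix J text, only a value of exactly 3 times ULN would meet the Table 2 limit.
- Creatinine: values above 1.5 times ULN are excluded and the Table 2 limit is 177 μmol/L. A value within the entry rule reaches that limit only if ULN is at least 177 / 1.5 = 118 μmol/L.
- GGT, ALP, LDH, BUN, bilirubin raised in isolation, haematocrit, haemoglobin, WBC, eosinophils, ANC and platelets: no numeric entry limit. Exclusion rests on the investigator's judgement of clinical significance.

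**3. How large could the effect be?**

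The documents give none of the following, so all are assumptions: b, the share of patients beyond a limit at baseline (1% to 5%); persistence on treatment (90%, equal across arms); and new-onset risk p (3% on drug, 1% on placebo).

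Displayed rate = 0.9b + (1 − b)p. The difference between arms is therefore (1 − b)(3% − 1%).

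| b | Drug | Placebo | Ratio | Difference (points) |
|---|---|---|---|---|
| 0% | 3.00% | 1.00% | 3.00 | 2.00 |
| 1% | 3.87% | 1.89% | 2.05 | 1.98 |
| 3% | 5.61% | 3.67% | 1.53 | 1.94 |
| 5% | 7.35% | 5.45% | 1.35 | 1.90 |

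With other assumed risks (8% and 2%), b = 5% and full persistence, the displayed rates are 12.6% and 6.9%. The ratio falls from 4.0 to 1.83 and the difference from 6.0 to 5.7 points. The pattern is the same: the ratio moves a lot and the difference very little.

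Noise, for b = 3% and 100 patients per arm: persistent carriers make up 0.9 × 3% = 2.7% of each arm. The standard deviation of the between-arm difference in their number is √(2 × 100 × 0.027 × 0.973) ≈ 2.3 patients. The expected excess of new cases is 100 × 0.97 × 2% = 1.94 patients.

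If only patients not beyond the limit at baseline are counted, the expected rates are 3% and 1% whatever b is, and the ratio is 3.0. At b = 3% the denominator falls from 100 to about 97 per arm.

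**The case against.** The strongest reply is that this is a choice of tabulation in a descriptive table. SAP 8.8 specifies neither a ratio nor a test. On the illustration's own inputs the arms go from roughly 3 against 1 patients to roughly 6 against 4, which is the same excess of two. The baseline prevalence is assumed, and entry rules push it down: patients must be judged in good health on the basis of laboratory tests among other things, and clinically significant findings are excluded. Signal detection also has other routes, because laboratory results judged clinically significant are recorded as adverse events and summarised as treatment-emergent. All of this stands. It limits the weight of the point but does not supply the missing rate.

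A reader might infer that the SAP contradicts itself, since urinalysis and vital signs refer to baseline. The documents do not support that. The urinalysis rows use change alone. The vital-sign rule still counts a patient who starts at a systolic pressure of 180 mm Hg and rises by 20. Neither rule excludes patients already beyond a limit. The comparison shows only that the SAP looks back to baseline elsewhere.

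A reader might also infer that the present count should be replaced. That would remove from the table any patient who starts beyond a limit and worsens further, which is a real loss in a safety summary. The inclusive count also fits protocol 9.7, which compares all values with preset boundaries.

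**Conclusion.** The point holds as a modest gap in safety reporting. For chemistry and haematology tests without a numeric entry limit, the planned incidence mixes pre-existing and new abnormalities, and no other output separates them. The direction is certain if any patient is beyond a limit at baseline and stays there: the ratio moves toward 1 and noise is added. The size is not known. The ratios of 2.05 to 1.35 in place of 3.0 rest on assumed prevalence, persistence and risks, and on those same inputs the absolute difference shrinks only by the factor (1 − b).

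Two stronger readings are tempting, and the documents do not support them. One is that the table is biased for or against an arm: randomisation balances the background in expectation. The other is that a safety signal would be missed: no decision rule or error rate depends on this table, the absolute excess is nearly preserved, and ALT, AST and creatinine are largely protected at entry. A low-cost addition to the SAP is warranted, not a change to the existing count.

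**What to change.** In SAP 8.8, keep the existing all-patient table and add a second summary by treatment group for each chemistry and haematology test: the number and percentage of patients whose baseline value did not meet the Table 2 limit and who met it at any postbaseline assessment. The denominator is the patients with a baseline value not meeting the limit and at least one postbaseline value. A shift table of baseline against worst postbaseline status, using the Table 2 limits, would serve equally well. Show the baseline value in the listing, so that worsening from an already abnormal start is visible.

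The cost is a short addition to the SAP, one programming condition and one extra table, with denominators that vary slightly by test. No new data are needed.

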8.8.1. Laboratory Values Meeting Hy’s Law Criteria

All occurrences of possible drug-induced liver injury that meet Hy’s law criteria as defined in the Section 7.1.5.1 of the study protocol will be included in serious adverse events reporting.

8.9. Physical Examinations

Physical examinations will be performed at visits 1, 2, and 5. Any physical examination finding that is judged by the investigator as a clinically significant change (worsening) compared with a baseline value will be considered an adverse event, recorded on the CRF, and monitored as described in Section 7.1.2 of the study protocol.

Abnormal physical examination findings will be listed.

Weight and height will be summarized and listed with vital signs data.

8.10. Vital Signs

Vital signs (pulse, systolic and diastolic blood pressure, and body temperature) will be measured at each (visit 1 through 5). Weight will be measured at visits 1, 2, and 5. Any vital sign value that is judged by the investigator as a clinically significant change (worsening) from a baseline value will be considered an adverse event, recorded on the source documentation and transcribed onto the CRF, and monitored as described in Section 7.1.2 of the protocol.

Vital signs (including weight) values and changes from baseline to each visit and the Last Assessment will be summarized using descriptive statistics. The incidence of potentially clinically significant abnormal values will be summarized for selected vital signs using descriptive statistics. Baseline is defined as the last observed data before the administration of the first dose of the IMP (also see Section 4.2).

Table 3 specifies the criteria for identifying vital signs as potentially clinically significant abnormal values. Note that in order to qualify as potentially clinically significant abnormal, a value needs to meet both criteria below: ie, have a value beyond the criterion value and a change of at least the magnitude specified in the change relative to baseline column. The potentially clinically significant abnormal vital signs values will include all postbaseline values (including scheduled, unscheduled, and early withdrawal visits) for the summaries.

Table 3: Criteria for Potentially Clinically Significant Vital Signs

Vital Sign	Criterion value	Change relative to baseline
Pulse	≥120 bpm	Increase of ≥15 bpm
	≤50 bpm	Decrease of ≥15 bpm
Systolic blood pressure	≥180 mm Hg	Increase of ≥20 mm Hg
	≤90 mm Hg	Decrease of ≥20 mm Hg
Diastolic blood pressure	≥105 mm Hg	Increase of ≥15 mm Hg
	≤50 mm Hg	Decrease of ≥15 mm Hg
Temperature	≥38.3°C	Change of ≥1.1°C

bpm=beats per minute

Height will be measured at screening visit, and data will be listed in the vital sign listing.

8.11. Electrocardiography

Triplicate 12-lead ECGs will be collected at visits 1, 2, and 5. Any ECG finding that is judged by the investigator as a potentially clinically significant change (worsening) compared with a baseline value will be considered an adverse event, recorded on the source documentation and in the CRF, and monitored as described in Section 7.1.2 of the protocol.

For ECG variables, the mean of recorded results from the 3 measurements at a visit will be calculated. The mean results and mean changes from baseline to EOT and Last Assessment will be summarized using descriptive statistics. Baseline is determined based on the last set of observed data before the administration of the first dose of the IMP (also see Section 4.2).

For ECG findings, the worst value of recorded findings at a visit will be used for analysis. Baseline ECG findings and shifts (normal, abnormal not clinically significant, and abnormal clinically significant) from baseline to overall (worst value for a patient) and the Last Assessment (worst value of recorded findings from the last visit) will be summarized using patient counts.

8.12. Concomitant Medications or Therapies

Concomitant medications, treatments, or procedures will be collected up to the end of study.

All concomitant medications will be coded using the WHO Drug. The incidence of concomitant medications will be summarized using descriptive statistics by therapeutic class and preferred term. Patients are counted only once in each therapeutic class category, and only once in each preferred term category. The concomitant medications will include all medications taken after administration of the first IMP.

The subset of medications or therapies will be summarized by the indication categories as indicated in Section 5.5.

9. TOLERABILITY VARIABLES AND ANALYSIS

Tolerability was not specifically defined for this study.

10. PHARMACOKINETIC ANALYSIS

There are no prespecified pharmacokinetic endpoints.

Fremanezumab plasma concentration will be summarized using descriptive statistics at each planned sampling time point for each of the active treatment groups (samples from patients who received placebo will not be analyzed). The summary will be based on the safety analysis set. The plasma concentration will be listed by active treatments, scheduled visits and time points.

11. PHARMACOGENOMIC ANALYSIS

Pharmacogenomic analysis results will be summarized for each gene tested. An attempt will be made to correlate clinical observations (pharmacokinetics, safety, efficacy, or other effects) with the genotypes observed. Additional pharmacogenomic analysis may be conducted at a later time and will be reported in a separate addendum report.

This analysis is not included in this SAP.

12. BIOMARKER ANALYSIS

Biomarker analysis will include logistic regression, receiver operating characteristic curves, and summary statistics. Results will be reported separately. Measurements will be made using validated assays.

This analysis is not included in this SAP.

13. IMMUNOGENICITY ANALYSIS

A summary of immunogenicity results will be provided, and the incidence of immunogenicity will be calculated. The impact of immunogenicity on the pharmacokinetics profile, IMP efficacy, and clinical safety will be evaluated. This ADA impact analysis will be reported separately.

This analysis is not included in this SAP.

14. ANCILLARY STUDY ANALYSIS – WEARABLE SENSOR SUBSTUDY

A subset of patients (n=45, approximately 15 patients from each treatment group) from each pivotal study (TV48125-30056 and TV48125-30057), approximately 90 patients in total, will be asked to wear a sensor monitoring system (digital wearable device) on the wrist to track sleep patterns and activity patterns. These patients will be allowed to continue in the substudy during the long-term safety study (TV48124-30058).

Analyses for endpoints from the wearable sensor substudy will include summary statistics and

Results will be reported separately.

